9.4.3. Secondary Endpoint(s)

The secondary endpoint(s) of the study are:

- Change in KCCQ-CSS from baseline to Week 12 and Week 24
- Proportion of patients with ≥ 1 class improvement in NYHA Functional Class from baseline to Week 12 and Week 24
- Change in post-Valsalva LVOT-G from baseline to Week 12 and Week 24
- Proportion of patients with post-Valsalva LVOT-G < 30 mmHg at Week 12 and Week 24
- Duration of eligibility for septal reduction therapy (SRT) during the 24-week treatment period in patients who were eligible for SRT at baseline. Participants are classified as being SRT eligible if they have NYHA Class ≥ 3 AND resting or Valsalva LVOT-G ≥ 50 mmHg.
- Change in total workload during CPET from baseline to Week 24

Change in KCCQ-CSS and change in post-Valsalva LVOT-G from baseline to Week 12 and Week 24 will be analyzed using a mixed model repeated measures (MMRM) model with baseline as covariate, randomization stratification factors, visit, treatment group, and interaction terms of treatment by visit and baseline by visit. An unstructured covariance matrix will be specified.

Proportion of patients with ≥ 1 class improvement in NYHA Functional Class from baseline to Week 12 and Week 24 or proportion of patients with post-Valsalva LVOT-G < 30 mmHg at Week 12 and Week 24 will be analyzed using Cochran–Mantel–Haenszel (CMH) test stratified by randomization factors. Patient's Week 20 NYHA Functional Class will be used when Week 24 NYHA Functional Class is not available. Total duration of SRT eligibility (NYHA Class ≥ 3 AND resting or Valsalva LVOT-G ≥ 50 mmHg) during the 24-week treatment period will be analyzed using an ANCOVA model with treatment group and randomization stratification factor beta blocker use/no use as fixed effects adjusting for significant baseline characteristics. The p-value and 95% CI will be obtained using exact method. Adjustment of multiplicity of the primary and secondary endpoints is specified in [Section 9.4.1.1](#).

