For the proportion of patients with ≥ 1 class improvement in NYHA class at Week 12, Week 16 NYHA class will be used if Week 12 NYHA class is not available. Week 8 NYHA class will be used if Week 16 NYHA is not available. Patient will be considered as not achieving ≥ 1 improvement in NYHA class at Week 12 if no NYHA at Weeks 8, 12 and 16 is available. Similarly, Week 20 NYHA class will be used if Week 24 NYHA is not available. Patient will be considered as not achieving ≥ 1 improvement in NYHA class at Week 24 if Week 20 and Week 24 NYHA are not available. A sensitivity analysis will be performed by repeating Cochran–Mantel–Haenszel (CMH) test by assigning missing NYHA class at Weeks 12 and 24 as non-responders. Proportion of patients with ≥ 1 class improvement in NYHA class will be analyzed using CMH test stratified by randomization factors. The p-value and 95% CI will be obtained using exact method.

Subgroup analysis will be done by repeating the CMH test for each subgroup level without specifying stratifying by randomization stratification factors.

4. Proportion of patients with post-Valsalva LVOT-G < 30 mmHg at Weeks 12 and 24

For the proportion of patients with post-Valsalva LVOT < 30 mmHg at Week 12, Week 16 post-Valsalva LVOT will be used if Week 12 visit is performed but post Valsalva LVOT is not available. Week 8 post-Valsalva LVOT will be used if Week 16 is not available. Similarly, Week 20 post Valsalva LVOT will be used if Week 24 is performed but post Valsalva LVOT is not available.

Proportion of patients with post-Valsalva LVOT-G < 30 mmHg at Weeks 12 and 24 will be analyzed using Cochran–Mantel–Haenszel (CMH) test stratified by randomization factors. The p-value and 95% CI will be obtained using exact method.

Subgroup analysis will be done by repeating the CMH test for each subgroup level without specifying stratifying by randomization stratification factors.

- Total duration of SRT eligibility during the 24-Week treatment period in patients who were SRT eligible at baseline

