7.9.1. Analysis of the Exploratory Efficacy Endpoint

The same ANCOVA model specified for the primary endpoint will be used to analyze the endpoints from CPET and continuous CMR measurements that are only assessed once post randomization. Body weight will not be included in the model to analyze CMR parameters. The same MMRM model will be used to analyze the continuous endpoints measured at multiple visits post randomization. CMH test stratified by randomization factors will be used analyze endpoints evaluation proportion of responders or binary outcomes.

Proportion of responders at each week will be summarized. Responders that are defined based on NYHA classification or LVOTs will be assigned after data handling in case there are missing NYHA class or LVOT assessments. Missing NYHA classification or LVOT value will be imputed the same way as that for the secondary endpoints that are based on NYHA classification or LVOT value. Patient will be treated as non-responder if patient's response status can't be determined due to the missing NYHA classification or LVOT assessments (after the imputation above) or clinical visits not performed after the patient early terminates from the study. Proportion of responders will be analyzed using Cochran–Mantel–Haenszel (CMH) test stratified by randomization factors. The p-value and 95% CI will be obtained using exact method. Proportion of patients remaining SRT eligible at Week 24 will be analyzed using logistic model regression model stratified by beta blocker use/non-use adjusting for significant baseline characteristics. The model will include treatment as fixed effect and baseline characteristics as covariates. Covariates measured as continuous will be introduced to the model as continuous variable. Stepwise model selection method will be used based on the default stay or entry level of 0.05 to evaluate significant baseline covariates. Supportive analysis using CMH stratified by randomization factor (beta-blocker use/non-use) will be performed. Another supportive analysis of proportion of patients SRT eligible at each visit will be provided using a repeated measure logistic regression model with treatment, visit, treatment by visit and significant baseline characteristics from the model above. Time to first SRT ineligible in patients who are SRT eligible at baseline will be analyzed using Kaplan-Meier method.

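### A missing Week 24 or Week 12 NYHA class is filled from a neighbouring visit whatever the reason, so a patient who improved and then died or left the study can count as a responder at Step 3 or Step 8

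*SAP*

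**What the plan says.** The proportion of patients improving by at least one NYHA class is tested at Week 24 (Step 3) and Week 12 (Step 8) of the fixed sequence in SAP 7.6. SAP 7.8.1 item 3 sets the missing-data rule.

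- **Week 24:** "Similarly, Week 20 NYHA class will be used if Week 24 NYHA is not available". Protocol 9.4.3 agrees: "Week 20 NYHA Functional Class will be used when Week 24 NYHA Functional Class is not available".
- **Week 12:** "Week 16 NYHA class will be used if Week 12 NYHA class is not available", and then "Week 8 NYHA class will be used if Week 16 NYHA is not available". The protocol has no Week 12 rule.
- **Non-response** is assigned only when the substitute visits are missing as well.
- **Sensitivity analysis:** the CMH test is repeated with every missing Week 12 or Week 24 class set to non-response.

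None of these sentences depends on why the class is missing. Other rules in the same plan do take this into account:

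- **Gradient responders (SAP 7.8.1 item 4):** "Week 20 post Valsalva LVOT will be used if Week 24 is performed but post Valsalva LVOT is not available".
- **SRT duration (SAP 7.8.1):** neighbouring visits fill intermittent gaps. Visits that did not happen after early termination are scored as SRT eligible, which is the unfavourable state.

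SAP Table 5 defines estimands for pVO2 only. No strategy for death or study withdrawal is given for NYHA class.

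**The concern.** Death or departure from the study is not an improvement in functional class. Under this rule a patient whose last class before the event was better than baseline keeps that success at a visit that never took place. Steps 3 and 8 are confirmatory: failure at Step 3 ends testing of Steps 4 to 11, and failure at Step 8 ends Steps 9 to 11. If more aficamten than placebo patients have improved by the earlier visit, as the trial expects, equal late loss in the two arms adds more carried-forward successes to the aficamten arm. The same patient could count as a success at Step 3 and be scored unfavourably after leaving at Step 6, and the SAP does not explain the difference.

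**Working it through.** **The plan's own figure.** The documents give no response rate, power or missing-data rate for NYHA. The nearest figure is the power for pVO2 (SAP 3.3.1): difference 1.5, SD 3.5, 135 per arm, 10% missing. Evaluable per arm: 135 × 0.9 = 121.5. Then 1.5 / (3.5 × √(2/121.5)) = 3.34, and 3.34 − 1.96 = 1.38, which gives 91.6% power. The stated figure of more than 90% is reproduced. The 10% is therefore a rate of missing pVO2, not of leaving the study.

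**Step 1: who is affected.** NYHA is recorded at every visit and at the early discontinuation (ED) visit (protocol 1.3). ED records are assigned by study day (SAP Table 8), and a scheduled visit takes priority within its window (SAP 5.7.7). Week 20 is scheduled on day 141 and Week 24 on day 169.

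| Improved at Week 20, then | Class used for Week 24 | Affected? |
|---|---|---|
| Stops study drug, stays in the study | Observed at Week 24 | No |
| Leaves, ED visit on days 155–196 | Observed at the ED visit | No |
| Leaves, ED visit on days 142–154 | Scheduled Week 20 record | Yes, responder |
| Dies, or leaves with no later record | Week 20 record | Yes, responder |

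The same holds for Week 12: an ED visit on days 71–98 supplies the class. One on days 58–70 does not, because the scheduled Week 8 record takes priority.

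**Step 2: size.** Assumptions: study loss of 10% (borrowed from pVO2 as an upper value), spread evenly over 24 weeks, and 50% v 25% improved at the earlier visit. The two response rates are not in the documents.

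- Lost in the 4 weeks between Week 20 and Week 24: 0.10 × 4/24 = 0.0167. That is 0.0167 × 270 = 4.5 patients, or 2.25 per arm.
- Counted as responders: 2.25 × 0.50 = 1.13 on aficamten and 2.25 × 0.25 = 0.56 on placebo.
- Inflation of the difference: 0.0167 × (0.50 − 0.25) = 0.0042, or about 0.4 points. Net, this is roughly half a patient.
- With 5% loss: about 0.2 points. With 40% v 25% improved and 10% loss: 0.0167 × 0.15 = 0.0025, or about 0.25 points.
- The Week 24 window opens on day 155, 14 days before day 169. If ED visits supply a class for everyone leaving in that second half of the 28-day gap, 0.4 × 14/28 = 0.2 points.

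The gap from Week 8 to Week 12 is also 4 weeks, so the figures are the same at Step 8.

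This count starts at the scheduled visit. A patient who leaves just before it, on days 127–140, and whose ED record stands in for Week 20 would also be carried forward. On the same assumptions these 14 of 168 days add at most 0.10 × 14/168 × 0.25 = 0.2 points. With every ED visit made, the total is then 0.2 + 0.2 = 0.4, no more than with none made.

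**Step 3: could it change the test?** This illustration uses an unstratified two-sided Fisher test with 135 per arm, placebo assumed at 34/135 (25%), and reclassification in the aficamten arm only. The smallest significant aficamten count is 50/135.

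| Aficamten responders | Reclassified patients needed to lose significance |
|---|---|
| 54/135 (40%) | 5 |
| 61/135 (45%) | 12 |
| 68/135 (50%) | 19 |

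At 54/135, p is 0.013. It becomes 0.036 after 3 reclassified patients and 0.065 after 5. Step 2 puts the expected number in that arm at about 1.

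**The case against.** **Stopping treatment is not leaving.** A reader might infer that anyone who stops study drug for an adverse event before Week 24 is scored as a success. The documents do not support that. Protocol 4.1 follows patients whether or not they continue study drug, and 7.2.1 encourages them to stay for the remaining visits. Such a patient normally has an observed Week 24 class. This objection stands and limits the point to death and study exit.

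**The 10% is not study loss.** A reader might take it as the drop-out rate. It also covers invalid exercise tests and patients unable to exercise, who may attend Week 24 and have NYHA recorded. SAP 7.7.1 expects few missing Week 24 tests and very few deaths. This stands, so 0.4 points is an upper value.

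**The alternative analysis is already planned.** The sensitivity analysis with missing counted as non-response will show any dependence on substitution. This stands as mitigation, but that analysis does not decide Steps 3 and 8.

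**It is a choice of estimand.** Calling the effect inflation presumes that leaving means failure. For a patient who leaves alive, a class observed four weeks earlier may be a fair guess under a treatment-policy view. That is arguable, but no NYHA estimand is stated to support it, and it does not cover death. Nor is leaving always scored as success: late leavers who had not improved are non-responders. The rule applies to both arms, so the direction of bias depends on where the late leavers fall.

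**The comparators are imperfect.** Item 4 does not say what happens when the target visit was not performed, so it shows that the condition was considered but is not a complete model. A reader might also cite SAP 7.9.1, which scores exploratory responders as failures for "clinical visits not performed after the patient early terminates from the study". That clause applies only when status is still undetermined after the same substitution, so it does not plainly contradict item 3.

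**Conclusion.** The point holds in a narrow form. As written, the rule makes a confirmatory responder of a patient who improved at Week 20 (or Week 8) and then died or left with no NYHA record in the target window. This includes patients whose ED visit falls too early to enter that window.

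The effect is at most about 0.4 percentage points in the responder difference, and about 0.2 if ED visits cover the second half of the gap. These figures rest on borrowing 10% as an upper value for study loss, even spread over time, equal loss in the two arms, and assumed rates of 50% v 25%. A clear treatment effect would survive, and only a result close to the 0.05 threshold could change. This is a cheap improvement, not a threat to the trial's conclusions.

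**What to change.** Amend SAP 7.8.1 item 3 and the matching sentence in protocol 9.4.3 before unblinding, so that the analysis deciding Steps 3 and 8 works as follows:

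- Use the neighbouring visit only if the patient is alive and still in the study at the target visit.
- Classify a patient who died or left the study with no NYHA record in the target window as a non-responder.
- Keep the analysis with all missing classes as non-response as the sensitivity analysis.

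The cost is one sentence in each document. Visits, data collection, sample size and the pVO2 analysis do not change. Responder rates fall slightly in both arms, with a small loss of power. As an illustration with 135 per arm, assumed rates of 45% v 25% and 2% late leavers in each arm, the rates become 0.45 × 0.98 = 44.1% and 0.25 × 0.98 = 24.5%, and power falls from 93.6% to 92.8%.

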5.2. Exclusion Criteria

Patients will be excluded from the trial if any of the following criteria apply:

- 201. Significant valvular heart disease (per investigator judgment).
 - a. Moderate-severe valvular aortic stenosis and/or regurgitation.
 - b. Moderate-severe mitral regurgitation not due to systolic anterior motion of the mitral valve

202. Documented history of current obstructive coronary artery disease (>70% stenosis in one or more epicardial coronary arteries) or documented history of myocardial infarction.
203. Known or suspected infiltrative, genetic or storage disorder causing cardiac hypertrophy that mimics oHCM (eg, Noonan syndrome, Fabry disease, amyloidosis).
204. Prior treatment with cardiotoxic agents such as doxorubicin or similar.
205. History of LV systolic dysfunction (LVEF <45%) or stress cardiomyopathy at any time during their clinical course.
206. Has any ECG abnormality considered by the investigator to pose a risk to patient safety (eg, second degree atrioventricular block type II).
207. Documented paroxysmal atrial fibrillation during the screening period.
208. Paroxysmal or permanent atrial fibrillation is only excluded IF:
 - rhythm restoring treatment (eg, direct-current cardioversion, atrial fibrillation ablation procedure, or antiarrhythmic therapy) has been required ≤ 6 months prior to screening
 - rate control and anticoagulation have not been achieved for at least 6 months prior to screening
209. History of syncope or sustained ventricular tachyarrhythmia with exercise within 6 months prior to screening.
210. ICD placement within 3 months prior to screening or planned ICD placement during the trial.
211. History of appropriate ICD discharge for life-threatening ventricular arrhythmia within 6 months prior to screening.
212. Has been treated with septal reduction therapy (surgical myectomy or percutaneous alcohol septal ablation) or cannot postpone plans for septal reduction therapy until after the trial period.
213. Inability to exercise on a treadmill or bicycle (eg, orthopedic limitations).
214. Documented room air oxygen saturation reading <90% at screening.

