8.1.4. Week 24: End of Treatment Visit

Week 24 is defined as the EOT visit and includes assessments and procedures critical for analysis of the trial's endpoints. These assessments are outlined in the Schedule of Activities. Additionally, the following should be considered in advance of Week 24:

- Contact patients shortly before the Week 24 EOT visit to confirm their ability to perform the CPET, and schedule the procedure to ensure it is completed within the protocol-defined window
- For patients temporarily unable to exercise on the treadmill or bicycle (whichever modality was used at baseline) due to an adverse event (eg, ankle sprain, upper respiratory infection, migraine), but not due to HCM symptoms, or if the site is unable to perform the CPET (eg, equipment malfunction), then the Week 24 visit may be postponed by up to 4 weeks and those patients should continue to receive IP until the visit
- Schedule CMR imaging for sub-study (if applicable)
 - For patients who provided consent and completed baseline imaging at screening, schedule the CMR imaging to ensure it is completed within the protocol-defined window. The baseline CMR should be performed within the 6-week screening period prior to randomization.

- The EOT CMR should be performed after the Week 20 visit, but prior to the last dose of IP at Week 24.
- If necessary, the Week 24 visit may be split across two consecutive days within the visit window. If the visit is split, all assessments, except the CPET, should occur on the first day of the split visit. The CPET should occur on the second day of the split visit. Dosing will occur on site on both split visit days.

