9.4.1.1. Multiplicity Adjustment

The null hypothesis for the primary and secondary efficacy variables in the FAS will be tested in the pre-specified order using a closed testing procedure.

For preservation of the overall type I error rate at two-sided 0.05 for the primary and secondary endpoints will be tested in the following specified order using a closed testing procedure. If the primary endpoint achieves statistical significance at two-sided $p \leq 0.05$, then secondary endpoints will be tested with two-sided 0.05, with their testing being in the sequential order of KCCQ-CSS change from baseline, proportion of patients with ≥ 1 NYHA functional class improvement, post-Valsalva LVOT-G change from baseline, proportion of patients with post-Valsalva LVOT-G < 30 mm Hg, and duration of SRT eligibility for participants who are SRT eligible at baseline, for each after 24 weeks of treatment; then KCCQ-CSS change from baseline, proportion of patients with ≥ 1 NYHA functional class improvement, post-Valsalva LVOT-G change from baseline, and proportion of patients with post-Valsalva LVOT-G < 30 mmHg, for each after 12 weeks of treatment; and lastly change from baseline to Week 24 in total workload. SRT eligibility is defined as resting or post-Valsalva LVOT-G ≥ 50 mmHg AND NYHA Functional Class ≥ 3 . The multiple testing procedure is illustrated in [Figure 1](#). The description of testing sequence will be detailed in the SAP.

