Patient SRT eligibility will be assigned after data handling in case there are missing NYHA class or LVOT assessments. Intermittent missing NYHA or LVOT will be imputed follows the same imputing method for missing Week 12 or Week 24; e.g., impute Week 16 NYHA if Week 20 NYHA is available or use Week 12 NYHA if Week 20 NYHA is not available. Patient will be treated as SRT eligible if SRT eligibility can't be determined due to the missing NYHA class or LVOT assessments or clinical visits not performed after patient early terminates from the study.

Total duration will be calculated as the number of days patients are SRT eligible, from the date of the randomization until Week 24. Total duration will be 24 weeks if a patient remains SRT eligible at all visits from baseline until Week 24 (regardless of whether a patient is SRT eligible at Week 24 or not). Because the SRT eligibility status of a patient may change during the study conduct, only intervals during which the patient is SRT eligible, will be summed. The start of the interval is the time of randomization (or resumption of SRT eligible status), and the end of the interval is the date prior to the visit when the patient becomes SRT not eligible.

SRT (Y/N) Case #	Week 2	Week 4	Week 6	Week 8	Week 12	Week 16	Week 20	Week 24	Duration SRT Eligible (Weeks)
1	N	Y	Y	Y	N	N	Y	Y	12
2	Y	Y	N	N	Y	N	N	Y	10
3	Y	Y	N	N	N	N	N	N	6
4	Y	Y	N	N	Y	N	Y	N	14
5	Y	Y	N	N	Y	N	Y	Y	14

Total duration of SRT eligibility during the 24 Week of treatment period will be analyzed using an ANCOVA model includes treatment and randomization stratification factor beta blocker use/non-use as fixed effects and significant baseline characteristics as covariates. Stepwise model selection method will be used based on the default stay or entry level of 0.05 to evaluate significant baseline covariates. Sensitivity analysis of the SRT eligible endpoints includes repeating the same ANCOVA analysis the area under the curve calculated using the numeric value assigned to the SRT eligibility at each visit and treatment duration until Week 24, where SRT eligibility is assigned to value of 1 and SRT not eligible is assigned to value of 0.

- Change in total workload during CPET from baseline to Week 24

The primary and sensitivity analysis for the total workload will follow the same analysis approach for the primary estimand of the primary endpoint.

Subgroup analysis will be performed similarly as specified for the primary endpoint.

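### The SRT-eligibility duration has no scoring rule for septal reduction performed on study, and no fixed end to its count

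*SAP*

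**What the plan says.** **Eligibility.** Protocol 9.4.1.1 reads "SRT eligibility is defined as resting or post-Valsalva LVOT-G" of at least 50 mmHg, together with NYHA class 3 or higher. Nothing in the definition refers to SRT having taken place.

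**The count.** SAP 7.8.1 gives these rules:
- "Total duration will be calculated as the number of days patients are SRT eligible, from the date of the randomization until Week 24".
- Of that span, "only intervals during which the patient is SRT eligible, will be summed".
- On when an eligible spell closes: "the end of the interval is the date prior to the visit when the patient becomes SRT not eligible".
- "Total duration will be 24 weeks if a patient remains SRT eligible at all visits from baseline until Week 24", whatever the status at Week 24 itself.
- Missing values are first filled from adjacent visits. Status that still cannot be determined counts as eligible, and so do "clinical visits not performed after patient early terminates from the study".

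**The Week 24 visit.** Under Protocol 8.1.4, if a temporary problem unrelated to HCM symptoms prevents exercise, or the site cannot run the test, "then the Week 24 visit may be postponed by up to 4 weeks". SAP 11.4 keeps a scheduled visit under its nominal label and applies no window to it.

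**SRT during the trial.** Exclusion criterion 212 (Protocol 5.2) keeps out patients who have already had SRT and anyone who "cannot postpone plans for septal reduction therapy until after the trial period". Protocol 4.1 continues follow-up whether or not the patient is still on investigational product. Neither document says how SRT performed between randomization and Week 24 enters the duration. The intercurrent events listed in SAP 7.7.1 are those that could prevent the Week 24 exercise test.

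**The concern.** The endpoint is meant to show how long a patient still qualifies for an invasive procedure. Protocol 2.2.1 itself describes that procedure as effective at lowering the gradient. A patient who goes through with it may therefore stop meeting the criteria because of the procedure, and the status variable cannot tell this from a response to drug. If the same patient leaves the study instead, the missing-data rule scores the later visits the opposite way, so attendance decides the direction.

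The second gap is the stopping point. A count in days that ends at a visit whose date can move will depend on things unrelated to SRT status, such as an ankle sprain or an equipment fault.

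This is Step 6 of the fixed sequence in SAP Table 4. If it fails, the four Week 12 tests (Steps 7 to 10) and total workload (Step 11) are not tested. The analysis uses only patients eligible at baseline, so each patient's value carries more weight than in the full analysis set. The planned area-under-the-curve sensitivity analysis uses the same eligible/not-eligible status and does not address either gap.

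**Working it through.** **Rule as a formula.** Let the status at each visit t = 0, 2, 4, 6, 8, 12, 16, 20 weeks hold until the next visit, with baseline eligible and the count ending at T. Then duration = sum of (next visit − this visit) over visits with status eligible. The nominal schedule has T = 24.

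**The SAP's own examples (T = 24).**

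| Case | Eligible spells | Rule | SAP table |
|---|---|---|---|
| 1 | 0–2, 4–12, 20–24 | 2 + 8 + 4 = 14 | 12 |
| 2 | 0–6, 12–16 | 6 + 4 = 10 | 10 |
| 3 | 0–6 | 6 | 6 |
| 4 | 0–6, 12–16, 20–24 | 6 + 4 + 4 = 14 | 14 |
| 5 | 0–6, 12–16, 20–24 | 6 + 4 + 4 = 14 | 14 |

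The always-eligible value of 24 and Cases 2 to 5 reproduce. Case 1 does not. Twelve appears only if the interval from randomization to Week 2 is dropped, which contradicts the stated start at randomization. Carrying status backward, or a trapezoidal area, gives 14 for Case 1 but fails Cases 2 to 5.

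**If the count ends at a Week 24 visit held at week 28 (T = 28).**
- Anyone eligible at Week 20 but not at every visit gains 28 − 24 = 4 weeks. Cases 4 and 5 go from 14 to 18.
- The always-eligible patient would sum to 28 but is fixed at 24.
- Of all 128 status patterns over Weeks 2 to 20, three others exceed 24: ineligible only at Week 2, only at Week 4, or only at Week 6. Each gives 28 − 2 = 26. If the Case 1 convention were intended, the Week 2 pattern would give 24 and two patterns would remain.
- In whole weeks on the nominal schedule, exceeding 24 needs a postponement of at least 3 weeks (27 − 2 = 25).
- Visit windows change this little. With Week 2 at Day 18 and Week 4 at Day 29 the gap is 11 days, and the maximum is (196 − 11)/7 = 26.4 weeks. The ordinary +7-day window alone gives at most (175 − 11)/7 = 23.4.

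With T fixed at 24, the same three patterns give 24 − 2 = 22 and no pattern exceeds 24.

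**On-study SRT, patient eligible at every visit beforehand.**

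| SRT performed after | Stays, below threshold from next visit | Leaves, no later visits | Weeks of difference |
|---|---|---|---|
| Week 4 visit | 6 | 24 | 18 |
| Week 8 visit | 12 | 24 | 12 |
| Week 12 visit | 16 | 24 | 8 |
| Week 16 visit | 20 | 24 | 4 |

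**Effect on an arm mean.** The documents do not give the share eligible at baseline. Assume 15% to 40% of 135 per arm: 0.15 × 135 ≈ 20 and 0.40 × 135 = 54 patients. One patient misscored by 12 weeks shifts the arm mean by 12/20 = 0.6 to 12/54 = 0.2 weeks. One 4-week postponement shifts it by 4/20 = 0.2 to 4/54 = 0.07 weeks.

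**The case against.** The best defence is that these are silences, not errors. Four readings go further than the documents allow.

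- **That the SAP treats SRT as a success.** It contains no such rule. The favourable score follows from the definition, and only if the patient stays in follow-up and falls below the gradient or NYHA threshold. For patients who leave, the default is unfavourable. This stands, and it is why the point is a missing rule.
- **That criterion 212 shows such patients are in the trial.** It does not. It admits patients who can defer SRT beyond the trial, and the synopsis likewise excludes those with plans for it during the trial. On-study SRT is admissible but probably uncommon.
- **That durations above 24 weeks follow from the text.** They need the count to run to the actual date of a postponed visit. The nominal labelling in SAP 11.4 is compatible with that, but 7.8.1 does not say so, and its examples are in nominal weeks. Even then, only three patterns exceed 24.
- **That a few patients could change the Step 6 result.** No standard deviation or assumed effect is given for this endpoint, so this cannot be shown. SRT in a placebo patient would shorten the placebo mean and work against the drug; SRT in an aficamten patient would favour it.

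It is also fair to say that counting an SRT patient as eligible is one of several defensible strategies. What does not stand is leaving the choice open. Two programmers following 7.8.1 could produce different values, and the worked table cannot settle it because Case 1 contradicts the text.

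**Conclusion.** The concern holds as a gap in specification with two parts. First, on-study SRT has no scoring rule, so the same event can score in opposite directions depending on attendance. Second, the count has no fixed end. On the actual-visit reading, a full postponement adds 4 weeks for anyone eligible at Week 20 but not at every visit, and can put a briefly ineligible patient (26 weeks) behind one who was never ineligible (24). The Case 1 discrepancy, 12 against 14 weeks, is certain and needs no assumption.

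The documents give no frequency of on-study SRT or postponement, so neither the net bias nor its effect on Step 6 can be sized. Its direction depends on the arm. The per-patient shift of about 0.6 to 0.2 weeks rests on the assumed 15% to 40% eligible share and a 12-week misscore. This is a minor point, worth settling because it is cheap and the step controls five later tests.

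**What to change.** Amend SAP 7.8.1 before unblinding:

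- **(a) On-study SRT.** For the analysis of this endpoint, score a patient who undergoes SRT as eligible from the procedure date to Week 24. This matches the SAP's unfavourable default for undetermined status. First confirm that the eCRF records the SRT date: Protocol 8.4.1.2 exempts some hospitalizations for surgery planned before consent from reporting, so capture through adverse events cannot be assumed.
- **(b) End of count.** End every patient's count at Day 168 (24 × 7 = 168, the day before the scheduled Day 169), whatever the actual date of the Week 24 visit.
- **(c) Worked table.** Reconcile Case 1 with the written rule. Until that is done, a pointer to the examples would not be a sufficient definition.

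The cost is a few sentences and slightly more derivation work, with no new visits. The drawback is reliance on the recorded SRT date.
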